# 3.5 IMPACT ON WORKLOAD ASSESSMENT (JUST IN SENEGAL)

One aim of this study is to understand how the addition of SAM to the CHW's workload affects the time allocation to other preventive or curative tasks. Toward this end, a time use assessment will be conducted among CHWs working in the intervention and control areas. Specifically, this analysis will provide information on differential time allocation between groups of workers on shared tasks (including management of cases of malaria, diarrhea and pneumonia), and average time to manage a SAM case for CHW in the intervention area.

Prior research suggests that self-administered time diaries are a method producing estimates of health worker's contact time with patients, which are similarly robust as the gold-standard time motion studies. Time diaries will be distributed to CHWs to fill out on purposively-selected work days. Diaries will be administered using a "left-behind" approach wherein respondents are given a diary to carry with them for the day, recording time spent on work activities as or just after they occur. A self-administered method will enable a larger sample of time observations than the use of recall interviews or surveyor observations. Every effort will be made to assure CHW of the confidentiality of their responses, so that the likelihood of their reporting ideal instead of actual time use is minimized.

The time diaries will contain open-intervals so that CHWs can fill in up to 2 activities completed at a time, and can enter in details about the activities. Coding of time activities will be done ex-post, with a standardized list of main CHWs activities developed in collaboration with a few CHWs and their supervisors. This list will have a cap of 30 main activities (including options for administrative paperwork, cleanup and non-productive time) to facilitate ex-post data coding. The study will be carried out during the peak period.

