The study will take place in the four health districts of the region: the districts of Matam, Thilogne, Kanel and Ranérou. According to the sampling strategy (see below), the study will work with 12 URENs and include 12 CHWs that are already trained in regular iCCM activities (case management of malaria, IRAs and diarrhoea, health promotion and prevention, and referrals of cases with complications).

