#### 2.2.2 SPECIFIC OBJECTIVES

- ✓ To determine if CHWs can treat SAM children and respect the SPHERE standards in an emergency setting;
- ✓ To assess whether coverage increases by including SAM treatment within iCCM package delivered by CHWs in an emergency setting;
- ✓ To assess whether CHWs can effectively use a combined/simplified protocol to treat SAM children in an emergency setting;
- ✓ To analyze cost and cost-effectiveness of three different models of SAM treatment.
- ✓ To analyze the impact of integrating SAM management in iCCM on CHW workload (just for Senegal)

[figure not shown]

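### Senegal workload study: diary days are picked purposively with no rule common to intervention and control areas, so the shared-task contrast can depend on which days are picked

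*Protocol*

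**What the plan says.** Protocol section 2.2.2 lists a workload objective for Senegal: "To analyze the impact of integrating SAM management in iCCM on CHW workload (just for Senegal". Section 3.5 sets out how it will be met:

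- **Groups:** "a time use assessment will be conducted among CHWs working in the intervention and control areas".
- **First output:** a between-group contrast, described as "differential time allocation between groups of workers on shared tasks (including management of cases of malaria, diarrhea and pneumonia".
- **Second output:** "average time to manage a SAM case for CHW in the intervention area", which concerns intervention workers only.
- **Days:** "Time diaries will be distributed to CHWs to fill out on purposively-selected work days".
- **Season:** "The study will be carried out during the peak period".
- **Safeguard against bias:** confidentiality, "so that the likelihood of their reporting ideal instead of actual time use is minimized".

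The protocol does not say what purpose guides the choice of days, who makes it, how many days each worker records, or whether the same rule or dates apply in both areas. It mentions no random or systematic selection and no weighting back to a working week.

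**The concern.** Time on a task over a working week is an average over days. If the work is uneven across days, that average depends on which days enter the sample. With purposive selection the chance of a day being included is unknown, so the analysis cannot afterwards recover a typical week.

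A contrast between two groups can survive this if both groups' days are picked in the same way, but nothing in the protocol requires that. The groups also differ in a way that invites different choices. Intervention workers treat SAM and control workers do not, so a day chosen because SAM children attend has no counterpart in control areas. The second output, time per SAM case, gives a practical reason to prefer such days in intervention areas.

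At stake is whether the Senegal study can say that adding SAM care takes time away from malaria, diarrhoea and pneumonia. Section 5.2 aims to change national policy on the tasks assigned to these workers, so the answer may be used.

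**Working it through.** **No figure to reproduce.** Section 3.5 gives no sample size, power or number of diary days. The check is a reading of the text plus an illustration.

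**Which output depends on day choice?**

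- *Shared-task contrast.* This compares time use between groups, so it depends directly on the mix of days in each group.
- *Mean time per SAM case.* This is averaged over SAM contacts. A day without a contact adds nothing to it, so day choice mainly affects how many contacts are timed. It is less sensitive.
- *Peak period.* It is stated for the whole time-use study, so it covers both groups. It restricts the season to which results apply and does not set the groups apart.
- *Confidentiality.* It addresses how honestly a day is recorded, not which day is recorded.

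**Illustration for the shared-task contrast.** Every input is an assumption; none comes from the protocol.

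- 5 working days a week, with SAM visits on d of them, d = 1 to 3
- SAM care takes a share s of time on those days, s = 20% to 40%
- shared tasks take b = 50% of time otherwise, and in control areas
- the day has fixed length, and SAM care displaces other work proportionally

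Formulas for intervention minus control, in percentage points of working time:

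- true weekly contrast = -b × s × d/5
- diaries on SAM-visit days only = -b × s
- diaries on other days only = 0

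| s | d | True | SAM-visit days only | Other days only |
|---|---|---|---|---|
| 20% | 1 | -2 | -10 | 0 |
| 20% | 3 | -6 | -10 | 0 |
| 30% | 2 | -6 | -15 | 0 |
| 40% | 1 | -4 | -20 | 0 |
| 40% | 3 | -12 | -20 | 0 |

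The ratio of the SAM-day figure to the true one is 5/d: 5 for d = 1, 2.5 for d = 2 and 1.67 for d = 3. The last two columns are extremes; a mixture of days falls between them.

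**Does weighting repair an excess of SAM-visit days?** Take s = 30%, d = 2. The shared-task share is 50% × (1 - 0.30) = 35% on SAM-visit days and 50% on other days. Weighted by their shares of the week, 0.4 × 35% + 0.6 × 50% = 44%. The contrast is 44% - 50% = -6 points, which equals the true value.

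**What if SAM care lengthens the day instead of displacing work?** Hours on shared tasks are then the same on every day, and a contrast in hours is not distorted by this route. A contrast in shares of time still is. Section 3.5 does not say which measure is meant.

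**The case against.** The strongest reply is that the protocol says only that days are chosen purposively. It does not say they are chosen around SAM visits, that the rule differs between areas, or that SAM work falls on particular days. Fixed weekdays, or avoiding training days, in both areas would fit the wording and could be harmless. Such operational detail often sits in a field manual or analysis plan, neither of which is at hand. The objective is also descriptive, one of five, and confined to Senegal.

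Much of this stands. The SAM-visit mechanism is an example and cannot be read out of the text. What does not stand is treating the matter as mere missing detail: the protocol itself commits to a non-probability choice of days for a between-group comparison, and a better alternative costs little.

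A reader might infer three stronger things that the document does not support:

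- *That restricting to the peak period biases the contrast.* It applies to both groups and limits generalisation only. Measuring when demand is highest is a defensible way to ask about crowding out, and section 3.5 makes no claim about the whole year.
- *That SAM workload will be overstated several-fold.* SAM's share of the week is not among the outputs listed, and any such multiple rests on assumed inputs and on every diary falling on a SAM-visit day.
- *That time on other illnesses will be understated.* This needs both the SAM-visit choice and a fixed-length day, and neither is stated.

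**Conclusion.** The point holds in limited form. Section 3.5 fixes a purposive choice of diary days with no rule common to both areas, so the between-group difference in time on shared tasks can depend on the days picked. Direction and size cannot be determined from the document. The assumed ranges above (true -2 to -12 points, observed anywhere from 0 to -20) show only that day choice alone could drive the result; they do not predict what will happen.

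The conclusion rests on two assumptions: that work is uneven across days, and that the choice of days may differ between areas. If one stated rule gave both groups a comparable mix of days, little of the concern would remain. The non-inferiority comparison of recovery in sections 3.1 and 3.2.1 is unaffected. This is a cheap improvement to one secondary component.

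**What to change.** - Within the peak period, draw diary days at random or systematically across the working week, and use the same calendar dates in intervention and control areas for the shared-task contrast.
- If extra SAM-visit days are wanted in intervention areas so that enough cases are timed, use those diaries only for the mean time per SAM case. Otherwise, weight them back to their share of working days in the intervention group, as in the calculation above. Stratifying both groups by SAM-visit day would not work, because control workers have no such days.
- State that the conclusions apply to the peak period.

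The cost is a list of dates and a few sentences in section 3.5, settled before diaries are handed out. The downside is that some sampled days will have no SAM visit, so slightly fewer SAM contacts are timed per diary day; the optional extra days make up for this.

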#### 3.6 RISKS OF IMPLEMENTATION

The cases enrolled in the study are not representative of the total population of the region, as only SAM cases treated by CHWs and HCs will be included in the study to evaluate the effectiveness of each model of SAM treatment.

Within the scope of the implementation of this research, we anticipate the following risks:

In Mali:

- The deterioration of the security situation in the intervention zone: AAH in partnership with AAG and the MoH will constantly monitor the status of the security situation and negotiate access if the need arises.
- Reduction of admissions in SAM cases at the CHW sites and in the supported healthcare centres: A Memorandum of Understanding (MoU) will be signed with the Health-Nutrition Partner in the intervention zone (Home-based Malaria Treatment - HMT) in order to maintain the continuity of community screening by community volunteers.
- Shortage of stock inputs: The project will put in place a buffer stock to ensure a continuous supply in case of stock shortages.
- Mobility of caring staff: The CHWs and HCDs who leave their positions will be replaced by the Health District in collaboration with the community authorities and will receive training aimed at quick deployment.

#### In Senegal:

- Shortage of RUTF inputs: the project is planning to reinforce the National Health Scheme, including the supply chain. A buffer stock of medical-nutritional products will be available.
- Political tensions due to the next presidential elections in 2019 and strike actions by the Health staff. Regular monitoring of the current political and social situation of the country will be carried out to prepare the teams in the field in the event of political tension and guarantee their security.

#### 4 STUDY PLANNING AND MANAGEMENT

#### 4.1 RESEARCH PARTNERSHIP

Underpinned by a collaborative partnership model, this project will be delivered by a strong consortium consisting of:

- Humanitarian organisation and consortium lead: AAH is a global humanitarian organisation and for almost 40 years has been at the forefront of the fight against hunger. Operating in nearly 50 countries, last year we reached over 20 million people through our humanitarian and development programmes.
- Academic research partner: EPINUT research group of the Complutense University in Madrid. EPINUT are regularly assessed by Spain's National Office for Research in the Ministry of Science, Innovation and Universities and recently went through a 3-year validation process.

#### - National research institute:

In Mali: INRSP is the National Research and Public Health Institute. Established in 1992, it is composed of highly qualified researchers and conducts public health research for MoH.

In Senegal: 2 research institutes from the Université Cheikh Anta Diop:

LARTES is the Research Laboratory for Social and Economic Transformation and is part of the *Institute Fondamental de l'Afrique Noire* (IFAN).

IPS is the Institute for Social Paediatrics.

In addition, the research will be supported by a collaborating implementation partner:

In Mali: Association d'Aide pour Gao (AAG) is a key partner of AAH in many research as well as operational projects.

In Senegal: Cellule de Lutte contre la Malnutrition (CLM) responsible for malnutrition care in the community in Senegal with strong ties to AAH.

#### 4.2 MANAGEMENT FRAMEWORKS

In both countries there is already a technical committee to follow up differences studies related to combined/simplified approach. These committees are under the lead of UNICEF together with the Ministries of Health. It has been created in several countries in West Africa. Other NGO working in management of acute malnutrition are part of them, as The Alliance for International Medical Action (ALIMA) or International Rescue Committee (IRC).

The study will be carried out with the supervision of a Steering Committee, composed of technical experts from the research consortium that is expected that will meet quarterly in order to plan and to ensure the good running of the study. An independent Scientific Advisor Committee composed of external members will bring relevant, independent, scientific expertise on a punctual basis and on specific topics, and advise on the way forward.

#### 4.3 ETHICAL CONSIDERATIONS

The study protocol will be submitted for review to the Spanish Ethical Committee assigned to the Complutense University of Madrid ("Comité de Ética Clínica Hospital Clínico San Carlos"), the Ethical Committees of academic institutions of both countries (Mali and Sengeal) and

The following principles will be adopted:

- Upon approval of the protocol, ACF in Mali/Senegal will inform the local and regional health authorities and the community representatives. The objective and procedures of the study will be explained to the caregiver. All the applicants will have the right to refuse participation in the study. Each CHW will be asked to read the voluntary and informed consent declaration in its entirety, slowly and in the local language of the participant. The CHW will then ask if the consent declaration was understood, and if there are any questions.
- √ The CHW will ask the caregiver if she or he agrees to participate in the study. At that
  moment, the opportunity to refuse participation in the study will be given to the
  applicant. The CHW will explain that it is possible to withdraw participation at any
  point in the study, without any repercussions on the patient or her/his family.
  Voluntary and informed consent for children will be given by the parents or legal
  guardian. A voluntary and informed consent form will be signed (or fingerprinted) by
  the principal caretaker, and, if present, the head of household. Those who refuse to
  participate will benefit from the same treatment as the other children, but their data
  will not be included in the study.
- Emergencies: Every participant in the study, whether in a control and intervention arms, will benefit from medical care in the event of medical complications linked to a change in their nutritional status during the study. The program will bear medical expenses related to these interventions. Acute malnutrition treatment is nevertheless available for free in every healthcare centre.
- Declaration of conflicting interests: Research team's sole interest is to contribute to an improvement in SAM treatment coverage and thus to an improvement in access to healthcare for remote communities with no treatment facilities, as well as to improve equity in iCCM care.
- Anonymity: precautions will be taken to ensure the anonymity of participants when collecting, managing and analysing data, and when disseminating the results. The forms containing data will be anonymized. SAM children will be identified by their SAM unique number. The data will be accessible to database managers, project managers, co-investigators and statisticians. All will be bound by terms of confidentiality.

#### 5 RESEARCH IMPACT

#### 5.1 EXPECTED RESULTS

This intervention it is expected to contribute to an improvement in access to care during humanitarian crises and a reduction in the number of children dropping out of acute malnutrition management programs. The advantages of this approach are the early diagnosis and care of malnourished children, which could lead to a reduction in the development of medical complications and impact on the health costs for households.

More cost-effective interventions will also allow health authorities to develop strategies for reaching a higher number of malnourished children during crises.

By improving CHW's capacities, and integrating SAM management into the iCCM package, the intervention also aims to have a positive impact on the management of other illnesses with a high mortality rate (diarrhoea, malaria and pneumonia).

The results generated by this research could provide key evidence for the full scale-up of this approach at country-level and in the Sahel region, improving SAM treatment coverage and contributing to a reduction in child mortality, particularly during humanitarian crises.

The specific results expected from the research are:

- 1) Effectiveness of a new intervention model with CHWs
- Evidence on the performance of the SAM care delivered by CHWs: Non-inferiority of the cure rate of children receiving care from the CHWs (greater or equal to the care provided by staff at HC).
- Evidence on the performance of the SAM care delivered using the simplified/combined protocol: Non-inferiority of the cure rate of children receiving care with this protocol.
- Evidence of an increase in the coverage of SAM treatment, in the health areas where treatment is available at HC level and CHW sites.
- 2) Contribution to the continuity of care
- Improvement of the continuum of care for SAM children across all levels of the health pyramid, starting from the Hospital Referral Health Centre (for SAM children with complications), to the HC (for SAM children without complications
   CMAM Approach), through to community-level care delivered by CHWs (for SAM children without complications - iCCM approach).
- 3) Cost-effectiveness of the intervention
- Cost-effectiveness analysis of the different models of SAM treatment: with the hypothesis of sharing the costs already in place for the iCCM intervention, but with an increase in the provision of services including SAM in the Community Primary Healthcare services package.
- Evidence on the reduction of costs for household and of treatment duration. We are seeking to remove barriers (such as geographical access and economic obstacles) to the provision of care in a humanitarian crisis context.

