#### 3.2 EFFECTIVENESS ASSESSMENT

#### 3.2.1 SAMPLE SIZE AND CLUSTERING

The sample size was calculated for a binary outcome (recover/not recover) assuming 5% non-inferiority margin, 80% power, 95% sensitivity, a recovery rate of 75% in the control group (as required by SPHERE standards), a recovery rate of 85% in the intervention group (as assumed in the similar ComPAS study described in the introduction section).

The number of clusters required has been calculated according to Hayes and Bennett formula assuming a 0.05 intra cluster correlation coefficient (same as in the ComPAS study). Including 10% loss to follow-up, this resulted in a sample size of 576 SAM children per arm requiring 6 clusters each (96 children per cluster). Therefore, total sample will consist of 1,728 children by country.

Each cluster will correspond to one treatment provider (HC or its group of CHWs) which means that there will be 6 groups of providers by arm. However, in order to avoid final real imbalance in clusters size, the unit of randomization will be the health center with an allocation ratio of 2:1:1. Using this approach, there will be 6 HC allocated to control arm (=6 providers) and 3 HC allocated to each intervention arm with their 3 groups of CHWs (=6 providers). This allocation ratio is based on the figures from our previous studies in Mali were each CHW treated more children on average than each HC during a 12-month period. If all arms involved the same number of HC, the intervention arms would recruit many more children than the control (children from 6 HC plus those of their CHWs).

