#### 3.2.3 DATA COLLECTION AND ANALYSIS

The comparability of the three arms is assumed due to randomization process but even so, it is intended that carers of the children enrolled will complete a short socio-economic survey at admission containing questions related to characteristics of household, livelihoods, hygiene practices and health services utilization according to the Demographic and Health Surveys Program methodology, as well as a Household Dietary Diversity Score. Those socio-economic variables will enable us to describe the sample and they will be used as possible confounders for the adjustment of regressions and risks analysis and to explore which of that has more impact on children's recovery in each arm.

To achieve our objectives, we will consider two main independent variables:

- Treatment provider (HC vs. HC+CHWs)
- Protocol applied in the case of CHWs areas (CMAM vs. Combined/Simplified).

The dependent variables to compare within SAM children (enrolled with MUAC<115mm in the three arms) will be the rates of: recovery (discharge as cured), default (children absent from treatment two consecutive follow-up visits), unresponsiveness (children not improving their nutritional status in two consecutive visits), transfer to inpatient treatment due to health complications and death.

Other variables to be compared will be severity at admission (MUAC measurement and presence of edema), prevalence of non-severe complications at admission and during treatment, treatment length and average daily weight and MUAC gain. Other routine information will be recorded monthly such as referral records and stock supplies.

Disaggregated data on the study subjects will firstly be recorded on paper (patient cards) by HC staff and CHWs according to the specific requirements of the MoH. The data will then be periodically reported by the supervisors via tablet using KOBO software which allows control of transcription errors improving data quality.

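### Section 5.1 states non-inferiority for CHW-treated children, but the only comparison fixed and sized is HC-only against a pooled HC+CHW arm, half of it planned as HC-treated

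*Protocol*

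**What the plan says.** Section 5.1 (Expected results) lists as its first effectiveness conclusion "Non-inferiority of the cure rate of children receiving care from the CHWs (greater or equal to the care provided by staff at HC"). The children in that sentence are those treated by CHWs, and the comparator is care by HC staff.

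Section 3.2.3 (Data collection and analysis) defines the variable for the provider question as "Treatment provider (HC vs. HC+CHWs"). The comparator group there is a mixture of both providers.

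Section 3.2.1 (Sample size and clustering) treats one provider, either an HC or its group of CHWs, as one cluster. It builds each intervention arm from "3 HC allocated to each intervention arm with their 3 groups of CHWs (=6 providers"), and the size per arm is given as "this resulted in a sample size of 576 SAM children per arm requiring 6 clusters each (96 children per cluster"). The same section counts children seen at the HCs of an intervention arm as part of that arm's recruitment. The assumptions are "assuming 5% non-inferiority margin, 80% power, 95% sensitivity, a recovery rate of 75% in the control group" and "a recovery rate of 85% in the intervention group". The protocol neither states nor sizes a comparison limited to CHW-treated children.

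**The concern.** The stated conclusion and the fixed comparison concern different children. Half of the planned intervention arm receives care from the same type of provider as the control arm. If that half performs like control, it pulls the arm's recovery rate toward control. In a superiority trial such dilution is conservative. In a non-inferiority trial it works the other way and makes a deficit in CHW care harder to see.

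The matter bears on use of the results: section 5.2 names adding SAM treatment to the tasks of CHWs as the policy change sought. A reader of section 5.1 would take the result as evidence on CHW care itself, when the comparison supports a statement about the service model.

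**Working it through.** **Inputs (section 3.2.1).** Control recovery 75%, intervention recovery 85%, margin 5 points, power 80%, intra-cluster correlation 0.05, loss 10%, 6 clusters of 96 per arm. The 95% figure, which the protocol labels sensitivity, is read as confidence. Sidedness is not stated, so both versions are shown.

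**1. The plan's own size.** Per arm without clustering: n = (z₁₋α + z₀.₈₀)² × (0.75×0.25 + 0.85×0.15) / (0.10 + 0.05)².
- One-sided 0.05: n = 87. The design effect at 96 per cluster is 1 + 95×0.05 = 5.75. This gives 497.7 children, or 5.18 clusters (5.28 at 86.4 evaluable per cluster after 10% loss). Rounded up to 6 clusters, 6 × 96 = 576, which matches.
- One-sided 0.025: n = 110, or 6.58 to 6.70 clusters, which rounds to 7. This does not match.
- The match at one-sided 0.05 also requires leaving out the extra cluster that the Hayes and Bennett formula adds (6.2 to 6.3 clusters with it).

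The 576 and the 5-point margin therefore belong to a contrast of 6 clusters against 6, that is, to the pooled arm.

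**2. CHW share.** s = 3×96 / 576 = 288/576 = 0.50.

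**3. Where the margin lies for CHW care.** Pooled difference = s × (CHW minus control) + (1 − s) × (in-arm HC minus control). If in-arm HCs perform like control HCs, the second term is zero, and a pooled deficit of 5 points equals a CHW deficit of 5/s:

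| CHW share s | CHW deficit at the pooled margin (points) |
|---|---|
| 0.50 | 10.0 |
| 0.60 | 8.3 |
| 0.67 | 7.5 |
| 0.80 | 6.3 |
| 1.00 | 5.0 |

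At s = 0.5, if in-arm HCs do 2 or 5 points better than control HCs, the deficit at the margin is (5 + 0.5×2)/0.5 = 12 or (5 + 0.5×5)/0.5 = 15 points. If they do 2 or 5 points worse, it is 8 or 5 points.

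**4. Chance of a false claim.** Take a true CHW deficit of exactly 5 points (70% against 75%), s = 0.5, and 86.4 evaluable children per cluster, so the design effect is 1 + 85.4×0.05 = 5.27. The pooled true difference is −2.5 points. Providers are treated as separate clusters, as the protocol counts them.
- Variance, pooled arm: [(0.70×0.30 + 0.75×0.25)/4] / 259.2 × 5.27 = 0.00202.
- Variance, control arm: 0.1875 / 518.4 × 5.27 = 0.00191.
- SE = √0.00393 = 0.0627.
- Probability of passing, one-sided 0.025: Φ(0.025/0.0627 − 1.96) = 0.059, about 6%.
- Probability of passing, one-sided 0.05: Φ(0.025/0.0627 − 1.645) = 0.106, about 11%.

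A test on CHW-treated children alone would pass at 2.5% and 5%. At one-sided 0.025 the pooled test passes about 3.6% of the time for a true CHW deficit of 8 points and 2.5% for one of 10 points.

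**5. What a CHW-only comparison could deliver.** With 3 CHW clusters against 6 control HC clusters, 85% against 75%, one-sided 0.025, power is 61% (86.4 per cluster) to 62% (96 per cluster). The pooled contrast of 6 against 6 has about 76% on the same basis.

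**The case against.** The strongest reply is that the sentence in section 5.1 is an expected result under a heading about an intervention model, and not an analysis rule. Sections 2.2.1, 3.1 and 3.6 all describe the target as a model of care, and for that target the pooled contrast is valid. The provider is identifiable, since clusters are defined by provider and the patient cards are completed by HC staff or CHWs. An analysis plan that is not at hand may contain a by-provider analysis. All of this stands, and it is why the remedy lies mainly in wording. It does not remove the mismatch, because section 5.1 names CHW-treated children and HC staff explicitly.

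A reader might infer more than the documents support:
- **That a 10-point CHW deficit would usually pass.** It would not. That deficit lies on the pooled margin, where the test passes only at its alpha.
- **That 10 points is the expected figure.** Section 3.2.1 says that in previous studies each CHW treated more children on average than each HC, so s may exceed 0.5. If the 12 CHWs named for Senegal in section 1.2 served the six intervention HCs (an assumption; the text does not say so), there would be two per HC, s would exceed 2/3, and the figure would fall below 7.5.
- **That the first specific objective is also undermined.** That objective is set against the SPHERE standards, which section 3.2.1 represents as 75% recovery. It is an absolute benchmark and not a non-inferiority claim.
- **That in-arm HC care always equals control care.** This is plausible for the arm with CHWs under the CMAM protocol. It is weaker for the combined/simplified arm, where section 3.2.2 sets different admission criteria and RUTF quantities without exempting HC patients. In both arms, families' choice of provider may change who attends the HC.

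**Conclusion.** The point holds as a mismatch between the conclusion stated in section 5.1 and the comparison fixed in section 3.2.3 and sized in section 3.2.1. The randomised comparison supports a conclusion about the HC+CHW model. It does not by itself support one about CHW-treated children, and using it that way errs in the anti-conservative direction.

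The size is moderate. The 5-point pooled margin corresponds to a CHW deficit of about 6 to 10 points for CHW shares from 0.8 down to 0.5. The false-claim rate at a true 5-point CHW deficit roughly doubles at s = 0.5. Both statements assume that in-arm HCs perform like control HCs; the error rates also assume equal cluster sizes and the protocol's correlation of 0.05. The argument is cleanest for the arm with CHWs under the CMAM protocol. The pooled contrast itself is not at fault.

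**What to change.** - Reword the first conclusion in section 5.1 so that the randomised result is non-inferiority of the HC+CHW model against the HC-only model.
- Report recovery separately for CHW-treated and HC-treated children in the intervention areas, each against control HCs, with confidence intervals that account for clustering by randomised HC. Label these results supportive and non-randomised, because carers choose the provider.
- State that nothing about CHW-treated children will be inferred from the pooled test alone.

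It is not advisable to make the CHW statement conditional on a formal pass of the by-provider comparison. That comparison is not randomised, rests on three CHW clusters per intervention arm, and has about 61–62% power at one-sided 0.025 under the protocol's own rates. Adjusting it for severity at admission could also remove part of the effect, since section 5.1 expects the intervention to bring earlier diagnosis.

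The cost is a narrower claim and a supportive analysis of limited precision. The data should need no new collection if the patient cards show which provider treated the child.
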